5. Potential benefit to subjects and others: All patients will be treated and followed following an ACS and will receive more intensive pharmacologic hyperlipidemia management which has traditionally resulted in improved patient outcomes. Patients will also be reimbursed \$50.00 for participation in the study, \$50.00 for the 90-day follow-up visit, and \$40.00 for each of the other follow-up visits to improve compliance and attainment of National Cholesterol Education Program (NCEP) and the latest ACC/AHA Lipid Lowering Therapy guidelines. The information obtained from this study could certainly develop as a viable strategy for our veterans. Successful completion of this study with acquired necessary experience may lead to development of this treatment strategy at one of the largest VAMCs in the nation.
6. Importance of the knowledge gained: The results of this study, apart from providing VP stabilization information from intensive LDL lowering, will principally advance the field of coronary atherosclerosis and VP healing.

4(j) Publication Policies and Planned Manuscripts

The study findings will be presented at national meetings and published in peer-reviewed medical journals. Before the publication phase, the study's objectives and other related facts will be presented for informational (not recruitment) purposes on the Cooperative Studies Program website at www.research.va.gov/programs/csp/ccta0002. Only general information will be provided without any participant-specific references. The Executive Committee will approve all topics for presentation or publication. It will review and approve all manuscripts and abstracts prior to submission. The Director, Hines CSPCC, must also approve every manuscript and abstract prior to publication.

4(k) Resources

All work including LDL-apheresis will be conducted on the premises of four study sites except that the EPC cell culture analysis will be done only at the Dallas VAMC:

1. Cardiac catheterization and PCI/IVUS-VH will be performed in the cardiac catheterization laboratory of the Dallas VAMC and other VA sites.

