A single treatment with LDL-apheresis has been demonstrated to have significant effect on arterial blood flow. Tamai et al. demonstrated that a single LDL-apheresis treatment increased nitrous oxide production and forearm blood flow²⁹. A single treatment with LDL-apheresis has also been shown to significantly reduce modified LDL particle, remnant-like particle-cholesterol, and C-reactive protein³⁰. In the LACMART study, one LDL-apheresis treatment over one year lowered the LDL of FH patients aggressively and demonstrated a significant reduction in the plaque area and increase in the minimum luminal diameter (MLD) with an annual angiographic and IVUS follow-up³¹. It also demonstrated that the benefits of LDL-apheresis are substantial when used in the setting of a statin pharmacotherapy. It is important to point out that in the FH population, the LDL cholesterol level in the medication-only arm did not change significantly from baseline ($174\pm 39\text{mg/dl}$ to $181\pm 53\text{mg/dl}$), and with LDL-apheresis it decreased from $213\pm 25\text{mg/dl}$ to $140\pm 27\text{mg/dl}$, which is much higher than the expected post-LDL-apheresis LDL levels expected in non-FH ACS patients. The details of atheroma regression are described in section 4(g), "Biostatistical Considerations".

Thus, we believe that the proposed ILLT strategy to jumpstart aggressive LDL reduction post-ACS is expected to have significant pathophysiologic and biochemical effects, in addition to significant atheroma regression expected with nearly 85% reduction in serum LDL levels. Though the vasoactive effects of LDL-apheresis are well known, its effect on EPC mobilization has never been studied. Our proposal will for the first time test this hypothesis and lay the foundation for a dedicated mechanistic study in the near future.

2(b) Relevance to Veterans Health

We believe that our proposed strategy would provide the basis for a large-scale study to evaluate clinical endpoints as a primary objective and ultimately lead to the development of a new strategy to attain more aggressive therapeutic lipid goals, and reduce CV events post-ACS, reduce the socioeconomic burden of ischemic heart disease, and improve the quality of life of our veterans.

3. Work Accomplished

This proposal is a logical extension of our ongoing work. We have:

[figure not shown]

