We expect to demonstrate a significant reduction in atheroma volume at 90 days by IVUS-VH (primary endpoint) because this study will have the most aggressive LDL lowering strategy in ACS patients ever tested in non-FH ACS patients. The 12-week time period is also the time point when early post-ACS CV events begin to increase, as seen in the PROVE IT-TIMI 22 trial⁹. Currently there are two clinical studies that have evaluated early (≤ 12 week) IVUS derived coronary atheroma regression and have demonstrated significant regression from baseline with pre-beta HDL²¹ and ApoA-1

Milano²⁰ infusions. The change in atheroma volume in the control arm was 2.8mm³ (increase) and that in the treatment arms were -12.18mm³ and -14.1mm³ with pre-beta HDL and ApoA-1 Milano therapies respectively. We also expect a robust response to ILLT with LDL-apheresis at 90 days. Our estimates of effect are much more conservative and have been described in detail in Section 4(g) under "Biostatistical Considerations".

4(b) Study Outcome Measures

The primary safety outcome measures will be the total number of and percentage of patients with major peri-PCI procedure adverse events, such as hypotension, angina, myocardial ischemia, myocardial infarction (if the patient is determined to have had unstable angina rather than non-ST-elevation MI at admission), cerebrovascular event (CVA), vermicular tachycardia, bleeding (at the PCI access and apheresis cannulation sites in the apheresis patients and at the PCI access site in the non-apheresis control patients), and death. The peri-PCI procedure is defined as encompassing the time of the PCI procedure and the time of the subsequent LDL-apheresis procedure for ILLT group vs. the time of the PCI procedure for SMT group. All LDL-apheresis-related adverse events in the ILLT group, including any minor expected events, will be recorded.

The secondary safety outcome measures will be the total number of and percentage of patients with statin-related abnormal liver function test events and statin-related muscle injury events, which could occur due to the maximum dose of statin drugs being given to both the ILLT group and SMT group patients. The statin-related muscle injury is defined as a muscle injury which cannot be attributed to a non-statin cause and which is evidenced by symptoms (muscle soreness, pain, or tenderness) and/or lab tests such as serum total creatine phosphokinase (CPK), CPK-MM, or myoglobin.

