4(g)(i). Expected Treatment Effect: There is only one study which examined the treatment of medication only (20mg Pravastatin or 10mg Simvastatin) vs. LDL-apheresis with statin medication on coronary plaque regression in familial hypercholesterolemia and published in 2002 Journal of American College of Cardiology³¹. The trial reported the net change of plaque area from baseline to one year follow-up. The changes were $-0.69 \pm 2.08 \text{mm}^2$ in the LDL-apheresis group vs. $0.88 \pm 1.75 \text{mm}^2$ in the medication only group. Two studies, which have primarily mobilized coronary atheroma LDL using HDL or its apoprotein, have shown similar magnitude of atheroma regression at 6-10 weeks, without directly lowering LDL levels. Given the expected 85% reduction in LDL after LDL-apheresis, we expected to observe a similar treatment effect for the primary effectiveness outcome of this study at 90 days.

4(g)(ii). Sample Size/Power/Level of Significance: To maintain 90% power to detect a Cohen's D effect size of 0.65 ($-0.38 \pm 2.08 \text{mm}^2$ in the LDL-A group vs. $0.88 \pm 1.75 \text{mm}^2$ in the medication only group) with the randomization scheme of 1:1, $\alpha = 0.05$, and a 20% drop-out rate, the pivotal study needs a sample size of 128.

4(g)(iii). Study Duration/Number of Sites: Four sites are considered for the purpose of generalizability and improved enrollment. Based on the enrollment rate in stage 1 of this trial, sites would expect to randomize 18 patients per site per year with an average rate of 1.5 patients per site per month. The average annual PCI volume during FY 2012 – 2013 reported by VA Cardiovascular Assessment and the data from CSP#571 currently enrolled at these 4 sites indicate that they will be able to meet or exceed the target of 18 participants per year. The percentage of patients with PCI who need to be randomized ranges from 3.5% to 5.0% across the four sites based on these reported annual PCI volume. About 30% of eligible subjects who meet the 3 major inclusion/exclusion criteria (ACS, LDL, and eGFR) need to be randomized in order to meet the accrual target. Dallas and Oklahoma City sites have ongoing LDL-apheresis capability and equipment on-site at the VA campus, and the Nashville and Denver sites have approved LDL-apheresis sites supported by device manufacturer (Kaneka) that will expedite the induction of these sites into the study.

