A total of 22 months is needed for 4 sites to randomize the total sample size of 128 in this second stage. The whole study duration for the second stage is expected to

be 46 months including 6 months of start-up, 22 months of enrollment, 6 months of follow-up, and 12 months of database search, study closure, and final data analysis. Upon approval, it is expected that the Dallas and Oklahoma City sites will begin recruitment almost immediately, followed by Nashville and Denver sites.

Estimated Enrollment for CCTA #0002 Phase II							
Site	PCI Volume as Reported by VA Cardiovascular Assessment, Reporting, and Tracking System for Cath Labs (CART-CL)		Annual ACS Indication, FY2014*	LDL > 70 mg/dL AND eGFR > 45 ml/min, FY2014*	Annual Eligible Patients	Monthly Eligible Patients	Monthly Accrual Target
	FY2013	FY2014					
Dallas	350	419	158	94	94	7.8	1.5
Oklahoma City	402	482	258	138	138	11.5	1.5
Nashville	250	313	173	110	110	9.2	1.5
Denver	132	210	115	58	58	4.8	1.5

*Eligibility criteria.

4(g)(iv). Statistical Analysis of Primary Effectiveness Endpoint:

The primary effectiveness outcome will be analyzed with intent-to-treat (ITT) approach by including all randomized patients regardless of crossover or drop-out. The change in total atheroma volume within a ≥ 20 mm long segment of the target coronary artery from baseline to 90 days will be analyzed using the two-sample t-test. We will define their change scores to be 0 if they do not have a 90-day atheroma volume measurement. Analysis of Covariance (ANCOVA) will be performed to evaluate the treatment effect on primary effectiveness outcome adjusting for age, pre-existing CAD, pre-existing diabetes, and baseline LDL levels.

4(g)(v). Statistical Analysis of Secondary Effectiveness Endpoints:

The intent-to-treat principle will also be applied to all the secondary effectiveness outcomes analyses.

- (1). The change of %NC component of atheroma from baseline to 90 days will be analyzed using the two-sample t-test. Similarly, the change scores for those who miss the 90 days follow up assessment will be set to zero. Analysis of Covariance (ANCOVA) will be performed to evaluate the treatment effect on primary effectiveness outcome adjusting for age, pre-existing CAD, pre-existing diabetes, and baseline LDL levels.

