## **Primary Effectiveness Outcome Measure**

The primary effectiveness outcome measure will be the change in the total atheroma volume within a  $\geq 20$  mm long segment of the target coronary artery from baseline to 12 weeks post-PCI. The measurement will be done via IVUS-VH at 2 time points (baseline during index PCI and 90-day follow-up).

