### **Sample Size Determination**

There is only one study which examined the treatment of medication only (20mg Pravastatin or 10mg Simvastatin) vs. LDL-apheresis with statin medication on coronary plaque regression in familial hypercholesterolemia and published in 2002 Journal of American College of Cardiology. The trial reported the net change of plaque area from baseline to one year follow-up. The changes were  $-0.69 \pm 2.08 \text{mm}^2$  in the LDL-apheresis group vs.  $0.88 \pm 1.75 \text{mm}^2$  in the medication only group. Two studies, which have primarily mobilized coronary atheroma LDL using HDL or its apoprotein, have shown similar magnitude of atheroma regression at 6-10 weeks, without directly lowering LDL levels. Given the expected 85% reduction in LDL after LDL-apheresis, we expect to observe a similar treatment effect for the primary effectiveness outcome of this study at 12 weeks.

The sample size of 30 patients for the first feasibility/pilot study leads to a power of 54% with  $\alpha = 0.05$  and the same effect size as reported in the published paper (Cohen's D effect size = 0.82 for  $-0.69 \pm 2.08 \text{mm}^2$  in the LDL-A group vs.  $0.88 \pm 1.75 \text{mm}^2$  in the medication only group). The power decreases to 38% with  $\alpha = 0.05$  and a more meaningful lower Cohen's D effect size of 0.65 by decreasing the difference of two treatment means by 20% ( $-0.38 \pm 2.08 \text{mm}^2$  in the LDL-A group vs.  $0.88 \pm 1.75 \text{mm}^2$  in the medication only group). The power decreases further to 31% by considering 20% drop-out rate with  $\alpha = 0.05$  and the Cohen's D effect size = 0.65.

The second stage of pivotal study is approved to obtain the 90% power to detect a Cohen's D effect size of 0.65 ( $-0.38 \pm 2.08 \text{mm}^2$  in the LDL-A group vs.  $0.88 \pm 1.75 \text{mm}^2$  in the medication only group) with the randomization scheme of 1:1,  $\alpha = 0.05$ , and a 20% drop-out rate, the pivotal study needs a sample size of 128.

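### Is the 90% power claim unsound because its effect size comes from one-year plaque area in familial hypercholesterolemia?

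*Protocol*

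**What the plan says.** Protocol 4(g)(ii) fixes the pivotal sample size at 128 "To maintain 90% power to detect a Cohen's D effect size of 0.65", with 1:1 allocation, alpha 0.05 and 20% drop-out. The underlying changes are −0.38 ± 2.08 mm² with LDL-apheresis and 0.88 ± 1.75 mm² with medication only. Section 4(g)(vii) uses the same inputs for the interim look: a difference of −1.26 and a pooled SD of 1.922.

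The source is a single trial in familial hypercholesterolemia whose control arm took pravastatin 20 mg or simvastatin 10 mg. Section 4(g)(i) says of it: "The trial reported the net change of plaque area from baseline to one year follow-up". Its published treated-arm change was −0.69 mm². The SAP (Sample Size Determination) explains that d was lowered from 0.82 to 0.65 "by decreasing the difference of two treatment means by 20" percent.

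The endpoint in this trial is different. The SAP states: "The primary effectiveness outcome measure will be the change in the total atheroma volume within a" segment of at least 20 mm, measured at about 90 days. Both arms receive atorvastatin 40-80 mg or equivalent.

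The link between the two is argued in 4(g)(i). Two short-term studies of HDL or its apoprotein are said to have shown regression of similar size at 6-10 weeks, and an 85% fall in LDL is expected. The section concludes: "we expected to observe a similar treatment effect for the primary effectiveness outcome of this study at 90 days". Section 4(a) gives those studies' results in mm³: "The change in atheroma volume in the control arm was" an increase of 2.8, against −12.18 and −14.1 in the treated arms.

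**The concern.** The standardized effect that drives N was observed on another measure (area, not volume), over another period (one year, not 90 days), in another population, and against a weaker control regimen.

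The control arm is the sharpest part. Of the planned 1.26 mm² difference, 0.88 mm² is growth of plaque in control patients. In the source trial, protocol 2(a)(vii) notes that "the LDL cholesterol level in the medication-only arm did not change significantly from baseline" (174 to 181 mg/dl). Control patients here take a stronger statin for a quarter of the time, so that growth may not recur. The reasons offered for a similar effect mostly concern regression in treated patients. No SD for 90-day volume change is given, although first-phase efficacy data had been collected and sent to FDA.

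If the true standardized effect were well below 0.65, the trial could miss a real benefit while describing itself as having 90% power.

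**Working it through.** **1. Reproducing the plan's figure.** Inputs are from Protocol 4(g)(ii).

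- Pooled SD = √((2.08² + 1.75²)/2) = 1.922.
- Source effect: (0.69 + 0.88)/1.922 = 1.57/1.922 = 0.82.
- Planned effect: (0.38 + 0.88)/1.922 = 1.26/1.922 = 0.656, stated as 0.65. The cut is consistent: 0.8 × 1.57 = 1.256.
- Two-sided t-test, alpha 0.05, power 0.90, d = 0.65: 50.7, so 51 per arm.
- Drop-out: 51/0.8 = 63.75, so 64 per arm and **N = 128**.
- Power with 51 per arm: 90.2% at d = 0.65; 90.6% at d = 0.656.

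The stated figure is exact for its inputs.

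**2. The rule for missing scans.** Section 4(g)(iv) says: "We will define their change scores to be 0 if they do not have a 90-day atheroma volume measurement". Suppose 20% are missing at random in each arm and all 128 are analyzed.

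- Difference = 0.8 × 1.26 = 1.008.
- Variance per arm = 0.8 × SD² + 0.16 × mean²: 3.484 (treated) and 2.574 (control). Root of the average = 1.740.
- d = 1.008/1.740 = 0.579; power with 64 per arm = 90.2%.

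The planned analysis therefore keeps the stated power under the plan's own inputs.

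**3. Area versus volume.** The change of unit alone does not alter d. If area is an average over a segment of fixed length, difference and SD scale together and d stays 0.656. The open question is whether d carries over to 90 days, this population and segments of varying length.

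**4. Where the planned difference comes from.** Control share = 0.88/1.26 = 70%. In the source trial it was 0.88/1.57 = 56%. It rose because the whole 20% cut was taken from the treated mean (−0.69 to −0.38). Keeping SD 1.922 and 51 per arm:

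| Control growth (mm²) | Power, treated −0.38 | Power, treated −0.69 |
|---|---|---|
| 0.44 | 57% | 84% |
| 0 | 17% | 43% |

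These figures show sensitivity to the assumption. They are not forecasts.

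**5. What the cited volume studies imply.** Taking the +2.8 mm³ control change for both, the differences are 12.18 + 2.8 = 14.98 and 14.1 + 2.8 = 16.9 mm³. With 51 per arm the effect detectable at 90% power is 0.648 × SD, so 90% power needs SD ≤ 14.98/0.648 = 23.1 or ≤ 16.9/0.648 = 26.1 mm³. The documents give no SD, so a range is assumed:

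| Assumed SD (mm³) | Power for 14.98 | Power for 16.9 |
|---|---|---|
| 20 | 96% | 99% |
| 25 | 85% | 92% |
| 30 | 70% | 80% |
| 38.4 | 50% | 59% |
| 45 | 38% | 47% |

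The 38.4 row is the one-year area SD multiplied by an assumed 20 mm (1.922 × 20). The documents do not make that conversion, and it relies on the same carry-over that is in question. It is not evidence about this trial.

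**The case for a change.** The strongest case for a change is that the 90% depends on an input nobody defends. On the 20 mm conversion, planned control growth is 0.88 × 20 = 17.6 mm³, against 2.8 mm³ in the short-term studies the protocol itself cites. The planned difference is then 25.2 mm³, against about 15.0 and 16.9. Section 4(a) calls the estimates conservative, but on this conversion that holds only for treated regression, not for the difference between arms. Repair looks cheap: quote the first-phase SD and show power over a range.

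Part of this stands. The support is indirect, mm² is compared with mm³ without SDs, and a sentence on the expected mm³ difference, control change and SD would have helped a reader.

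Three things limit it.

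- It is not true that nothing supports the carry-over. The short-term studies measured volume within 12 weeks, and the reference list describes one as a trial in ACS patients. Section 2(a)(vii) also argues that LDL after apheresis should fall further here than the 140 mg/dl reached in the source trial.
- The comparison cuts both ways. On the same conversion the planned treated change is only −0.38 × 20 = −7.6 mm³; the cited treated arms regressed 60% and 86% more (12.18/7.6 and 14.1/7.6). Power depends on the total difference and the SD, not on how the difference is split.
- The first-phase SD is not in the documents, nor is the number of paired scans. Even with all 30 patients contributing (28 degrees of freedom), its 95% limits would run from 0.79 to 1.35 times the estimate, too wide to settle whether the SD lies below about 23-26 mm³ unless the estimate is well away from that range.

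**Conclusion.** No change is needed. The plan delivers the power it states, for the effect size it states: 51 per arm, N = 128, 90.2% at d = 0.65, and still about 90% under the zero-change rule. The assumption is openly sourced and deliberately reduced, and borrowing from the only available apheresis trial is a fair trade-off where direct data are scarce.

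What remains is a thin written justification. Power for 90-day volume change is unknown. On the cited volume differences it ranges from 38% to 99% across assumed SDs of 20 to 45 mm³, with 90% reached at about 23.1 or 26.1 mm³. That range rests on the +2.8 mm³ control change applying to both studies and on 20% drop-out.

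Rewriting the paragraph would not alter N, the interim boundary, the primary test or how the result is read. A null result would be judged from the confidence interval for the difference in mm³, which uses the SD actually observed and owes nothing to the planning value.
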